a. Persons/groups who will review the data (study team; independent safety monitor, data monitoring committee or formal DSMB):

[name] and members of our research team will review the data

b. Data/events that will be reviewed

The data of adverse events and other safety related issues will be reviewed.

c. Frequency of review:

The data and safety review will be performed before and after the intervention, and the data will be viewed bi-weekly during intervention

d. Types of analyses to be performed

Any possible pattern of mistakes/errors will be carefully analyzed, and a plan of action will be made in order to prevent any future potential adverse events

e. Safety-related triggers that would cause the PI to stop or alter the study

The enrollment will be stopped immediately, and the study procedures will be reassessed if more than 20% of the participants experience any adverse effects.

- 1. Describe how adverse events and unanticipated problems will be ascertained and handled. Explain exactly which type of problems will be considered serious and reported to the IRB. The reporting timeframe should also be detailed.**

Any adverse events will be immediately reported to the PI and, if appropriate, to KUMC IRB per KUMC IRB policies. The PI will be notified immediately of chest pain, irregular pulse, fainting, shortness of breath, light headed/dizzy, excessive sweating, slurred speech, blurred vision, leg swelling, falls, or any other adverse events.

3. **Explain exactly what will happen if a patient experiences an adverse event or other problem**

Any participant who experiences chest pain, irregular pulse, fainting, shortness of breath, light headed/dizzy, excessive sweating, slurred speech, blurred vision, leg swelling, and falls will be placed on hold and the PI and [name] will make an appropriate decision about the participant's situation.

III. **Subject Participation**

A. Recruitment:

Study subjects will be recruited from 1) [name] rehabilitation clinic at the KU hospital 2) patients who are enrolled in Frontiers/Pioneers Research Participant Registries using the Healthcare Enterprise Repository for Ontological Narration (HERON) database at KUMC, 3) out-patients rehabilitation center in Kansas City area, and 4) flyers and advertisements. Potential study candidates can either provide their contact information to us or contact our team members by phone or email if they are interested in our study.

B. Screening Interview/questionnaire:

To determine the eligibility of participant, a phone screening will be conducted for each individual who is interested in participating in the study

C. Informed consent process and timing of obtaining of consent

A member of our research team will provide a participant with details and comprehensive information about the entire study and help the individual to make independent and thoughtful decision by providing sufficient time and answering questions. The process of informed consent will be taken place in a private room in our laboratory prior to any research related activity and if a participant agrees, he/she will sign a consent form approved by the IRB at University of Kansas Medical Center (KUMC). Each participant will be given a copy of the signed document. A participant should be able to understand the consent form and sign it; otherwise, they will be excluded. The originally signed consent form will be kept with the participant's confidential file in a locked file cabinet in the research laboratory.

D. Alternatives to Participation: N/A

E. Costs to Subjects: There are no costs to participants for being in the study.

F. How new information will be conveyed to the study subject and how it will be documented:

The participants will be told about anything new that might change their decision to be in this study. New information will be conveyed to participants through phone, email, or meeting. Our team will prepare a new consent form and thus, participants should be asked to sign a new consent form if this occurs.

G. Payment, including a prorated plan for payment:

Participants will not receive any payment in the study.

H. Payment for a research-related injury:

According to KUMC institutional disclaimer statement “If you think you have been harmed as a result of participating in research at the KUMC, you should contact the Director, Human Research Protection Program, [name], University of Kansas Medical Center, [name]. Under certain conditions, Kansas state law or the Kansas Tort Claims Act may allow for payment to persons who are injured in research at KUMC.”

IV. Data Collection and Protection

A. Data Management and Security:

Each participant will have a unique numerical code that will be used to identify participant’s documents and data. This code will be placed on the consent form and correspond with the participant’s data sheets. The consent form will have both participant’s name and the code. The consent form and other documents will be kept on locked cabinets in Neuromuscular Research laboratory at KUMC. REDcap website will be used to create and manage data collection forms. Participants’ data will be stored on a secure KUMC network drive which will be only accessible to the investigators and the members of research team.

B. Sample / Specimen Collection:

Blood drawing will take place in a clinical laboratory at Neurology Clinic in the KU hospital or at Neuromuscular research laboratory in KUMC. Blood sample will be drawn from each participant at two-time points in baseline and after completing the study. About 20 ml of blood will be collected into a tube containing heparin. The blood sample will be centrifuged at 1,800 g for 10 min at room in order to separate plasma from cells. Subsequently, blood sample will be stored at – 80 C⁰ until analysis at KUMC Diabetes Research Laboratory. Each blood sample tube be labeled by a code which does not has identifiable participant information.

C. Tissue Banking Considerations: N/A

D. Procedures to protect subject confidentiality:

Each participant will have a unique numerical code that will be used to identify participant’s documents and data. This code will be placed on the consent form and correspond with the participant’s data sheets. The consent form will have both participant’s name and the code. The consent form and participants’ documents will be kept on locked cabinets in Neuromuscular Research laboratory at KUMC. Also, participants’ data will be stored on a secure KUMC network drive which will be only accessible to the investigator (PI) and the members of research team.

E. Quality Assurance / Monitoring:

The data will be reviewed periodically by PI to make sure the data collected are accurate, consistent, complete and reliable.

V. Data Analysis and Reporting

A. Statistical and Data Analysis:

Statistical analysis will be conducted using SPSS statistical software. Descriptive statistics of frequency, mean, and standard deviation will be generated on the data collected during the study. Assumption of normal and variance of data will be assessed using Shapiro-Wilk test and Brown-Forsythe Levene test, respectively. For *primary hypothesis*, first, we will conduct the simple linear regression to determine whether there is a linear relationship between each factor and the outcome measure, which heart rate adaptation. If it is true that more than one factor is correlated

with outcome measure. As an Exploratory manner, we will conduct multiple linear regression to identify contribution of these factors to outcome measure and determine the factor that is strongly contributed to outcome measure based on contribution other factors. The level of significance for multiple regression will be set at 0.1 due to small sample of this pilot study. For *secondary hypothesis and exploratory aims*, the paired sample t-test will be utilized to assess difference in outcome measures pre- and post-training. The level of significance for paired-sample test will be set at 0.05.

B. Outcome:

Aim#1 expected results: For recruitment rate, we expect that one of every four candidate participants who are screened eligibility will enroll in the study (ratio of recruitment rate 4:1) as described in a past study in individuals with SCI.[183] For perception, we expect that participants will be satisfied with walk-training program in regard to time duration of walk-training and use of the assistive training device and time needs to step the assistive training device, and safety and comfortability of training. For compliance, we expect that participants will complete more than 80% of total training sessions. For retention, we expect that drop out during the study will be less than 20%. In regard to walking performance, we expected increase time of walk-training, treadmill walking speed, the number of stepping per session throughout training period.

Aim# 2 expected results: We expect that decreases in resting and exercise heart rate after 8 weeks of walking will show significant correlation with increased leg muscles activity, which will be stronger than its correlations with changes in cardiac autonomic function, leg muscle spasticity, or vital lung capacity

Aim#3 expected results: As compared to baseline measures, we expect that 8 weeks of walk-training program would decrease the levels of TC, HbA1c, CRP, and IL-6 and increase the level of HDL-C.

Exploratory aims expected results: We expected that 8 weeks of walk-training would 1) increase muscle strength of the lower extremities, 2) decrease muscle spasticity of the lower extremities and the level of depression, anxiety, and stress and 3) improve functional independence measure and quality of life in individuals with chronic SCI.

The Criteria for success or failure of the study will be depended on participants' compliance, the rat of drop out, and adverse events. For example, if compliance of participants is more than 80% and the rate of drop out is low, these will be considered success, vice versa. The study will be ended if most participants experience many adverse events due to the study.

C. Study results to participants:

We will not give any individual results to the participants since our study is not for diagnosis purpose. Participants will be notified when all results of the study are published.

D. Publication Plan:

Manuscripts and final reports will be published within one year after completing the study. The results will be published without any identifiable data for our participant.

VI. Bibliography / References / Literature Cited

1. Field-Fote, E., *Spinal Cord Injury: An overview*, in *Spinal Cord Injury Rehabilitation*, E. Field-Fote, Editor. 2009, F. A. Davis, 2009: Philadelphia, PA. p. pp. 3-87.
2. Nas, K., et al., *Rehabilitation of spinal cord injuries*. World J Orthop, 2015. **6**(1): p. 8-16.
3. Kirshblum, S.C., et al., *International standards for neurological classification of spinal cord injury (Revised 2011)*. J Spinal Cord Med, 2011. **34**(6): p. 535-46.
4. *Spinal Cord Injury (SCI) 2016 Facts and Figures at a Glance*. J Spinal Cord Med, 2016. **39**(4): p. 493-4.

5. Phillips, W.T., et al., *Effect of spinal cord injury on the heart and cardiovascular fitness*. *Curr Probl Cardiol*, 1998. **23**(11): p. 641-716.
6. Warburton, D.E., et al., *Cardiovascular Health and Exercise Rehabilitation in Spinal Cord Injury*. *Top Spinal Cord Inj Rehabil*, 2007. **13**(1): p. 98-122.
7. O'Sullivan, S.B., T.J. Schmitz, and G.D. Fulk, *Locomotor Training*, in *Physical Rehabilitation*, G.D. Fulk and T.J. Schmitz, Editors. 2014, F.A. Davis Company: Philadelphia, PA 19103. p. 444-484.

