EMG activity of leg muscles in a similar way to those seen in healthy individuals during walking [116]. The amplitude of EMG activity of leg muscles significantly increased after a period of walk-training and worsened after stopping training [116, 117]. In addition, individuals with high thoracic complete SCI showed activation of trunk muscles (back and abdominal muscles) while walking on a treadmill or overground [118]. These findings suggest that walk-training induces neuroplasticity of spinal cord circuits that can only be maintained by continuous walk-training. It is suggested that limb loading and afferent inputs during a treadmill walking can trigger spinal neuronal circuits to activate lower limbs and trunk muscles [109, 119].

When comparing to arm cycling or leg cycling exercise, upright walking can provide greater challenges to the cardiovascular and respiratory system that might induce greater cardiovascular and respiratory adaptive changes [120]. In healthy individuals, it was found that the value of heart rate and systolic blood pressure was significantly higher during treadmill exercise than bicycle ergometer exercise [121]. In addition, peak values of oxygen uptake and heart rate were significantly higher during treadmill exercise than during arm ergometer exercise [122]. Similar benefits in cardiovascular and respiratory systems have been observed in individuals with SCI. For instance, under the equivalent workload, the peak value of heart rate and oxygen uptake was higher during treadmill walking than that during stationary cycling in individuals with motor incomplete SCI [123]. Carvalho et al.[124] reported similar observations in individuals with complete quadriplegia after walking on a treadmill compared to endurance exercise in sitting position. Therefore, upright walking using BWSTT can be used as an alternative form of aerobic exercise in individuals with SCI.

B.6. Heart Rate Adaptation to Walking Exercise in People with SCI

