The timeline of this project will be one year (Table 1). First, we will begin recruiting and enrolling participants after the study is approved by Institutional Review Board (Human Subjects Committee) at the KUMC. Our goal is to enroll at least three participants a month in the study. We expect that we will meet our enrollment goal within 7 months of the study timeline. At 9 months, we expect that we will finish with providing training to participants. Second, we will analyze the blood sample and clinical assessments at 10 and 11 months. Finally, we will conduct statistical analysis at 12 months.

Table 1: Study timeline

Project activities	One-year timeline											
	1	2	3	4	5	6	7	8	9	10	11	12
Enrollment	█	█	█	█	█	█	█					
Intervention	█	█	█	█	█	█	█	█	█			
Outcome measures analysis										█	█	
statistical analysis												█

F. Risk/benefit assessment:

1. Physical risk:

During laboratory testing, participants might feel minor pain at the needle site, when blood sample is drawn from his/her body. Pain sensation will go away after blood drawing. Participants might feel muscles fatigue and sore, sweating, and physical discomfort during or after exercise. Also, there are possibility that participants may experience abnormal blood pressure response, fainting, irregular, fast, or slow heart rate during walking exercise, and in rare case, heart attack, stroke, or death. Throughout exercise session, we will carefully monitor participants to reduce the risk associated with walking exercise. We will immediately stop exercise if we observed any sign of risks on participants. Our research teams are trained to do CPR when it is need. Walk-training will be performed at moderate-intensity which has minimal risk and is convenient for individuals with SCI. Participants will get medical clearness from their physicians in order to participate in the study.

2. Psychological risk: N/A

3. Social risk: N/A

4. Economic risk: N/A

5. Potential benefit of participating in the study:

Participants may or may not benefit from participating in this study. Our research team hope that information gathered in this study will contribute to scientific knowledge of the benefit of walking exercise on cardiovascular health in individuals with SCI

G. Location where study will be performed:

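### The only trigger listed for stopping or altering the study weighs all adverse effects equally, so one heart attack, stroke or death does not by itself meet it from the fifth participant on

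*Protocol*

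**What the plan says.** Safety monitoring item e, just before Section III of the protocol, is the only entry under safety-related triggers for stopping the study or altering it: "The enrollment will be stopped immediately, and the study procedures will be reassessed if more than 20% of the participants experience any adverse effects."

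Section II.F.1 (Physical risk) names two very different groups of effects. The mild group includes pain at the needle site, and "Participants might feel muscles fatigue and sore, sweating, and physical discomfort during or after exercise." The serious group is "abnormal blood pressure response, fainting, irregular, fast, or slow heart rate during walking exercise, and in rare case, heart attack, stroke, or death."

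Other safeguards sit beside item e:
- Item 1 sends every adverse event to the principal investigator at once, and to the IRB where appropriate. It begins its list with: "The PI will be notified immediately of chest pain, irregular pulse, fainting, shortness of breath". The list ends with a catch-all for other adverse events.
- Item 3 acts on the individual. Participants with any of a list of symptoms, ending with "slurred speech, blurred vision, leg swelling, and falls will be placed on hold", wait for a decision on their own case.
- Data and safety are reviewed every two weeks during the intervention.

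Section V.B (Outcome) has a second study-level rule: the study ends if a majority of participants have many adverse events caused by it.

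**The concern.** A stopping rule should respond to the events that would make a reasonable team stop. Item e counts affected participants and ignores what happened to them, so a sore muscle and a stroke weigh the same. In a pilot of 19 people this works badly in two directions. One catastrophic event can fall below the threshold, and a handful of trivial ones can exceed it. The first matters more. Section II.F.1 foresees heart attack, stroke and death, yet after one of them no visible rule says that enrolment stops or that others' training pauses. Item e also does not say whether participants already enrolled keep training while procedures are reassessed.

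**Working it through.** **Inputs from the protocol.** The threshold is strictly more than 20% (item e). The planned number is 19 (Section II.C). Training is 24 sessions, three a week for eight weeks (Section II.E.2). The enrolment target is at least three a month, completed within 7 months (Section II.E.3). Item e does not say whether its denominator is participants so far or the planned 19, so both are checked.

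**Step 1: affected participants needed.** The smallest whole number c with c/n > 0.20 is:

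| Participants counted (n) | c | One affected participant as a share |
|---|---|---|
| 1 to 4 | 1 | 100% down to 25%: met |
| 5 to 9 | 2 | 20% down to 11.1%: not met |
| 10 to 14 | 3 | 10% down to 7.1%: not met |
| 15 to 19 | 4 | 6.7% down to 5.3%: not met |

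At n = 5, 1/5 = 20%, which is not more than 20%. With a fixed denominator of 19, 1/19 = 5.3%, 3/19 = 15.8% and 4/19 = 21.1%, so four are always needed. This step needs no event rate.

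**Step 2: the other study-level rule.** The Section V.B rule needs more than half of participants, each with many events. One event in one participant cannot meet it.

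**Step 3: how often the gap would matter.** Assume that heart attack, stroke or death affects a proportion q of participants, independently.
- At least one in 19 = 1 − (1 − q)^19. This is 1.9% of studies at q = 0.1%, 9.1% at 0.5% and 17.4% at 1%.
- Such events alone meet item e at some point, counting participants so far in enrolment order, in 0.40%, 2.0% and 4.0% of studies. With a fixed denominator of 19 the figure is below 0.01% even at q = 1%.
- Share of studies with such an event in which it does not itself meet item e: 1 − 0.0040/0.0188 = 79% at q = 0.1%, and 1 − 0.0404/0.174 = 77% at q = 1%.

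A rough check: a single event is equally likely to fall on any of the 19 participants and counts only for the first four, and 1 − 4/19 = 79%. These figures ignore the delay between enrolment and event. With one enrolment every 10 days and events spread evenly over 56 days, a single event precedes the fifth enrolment with probability (40 + 30 + 20 + 10)/56/19 = 9.4%. About 90% would then not meet the rule.

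**Step 4: minor effects, on the literal reading.** If a proportion p of participants has any adverse effect (assumed), the chance that item e is met is:

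| p | Judged on all 19, P(X ≥ 4), X ~ Bin(19, p) | Judged on participants so far, at some n |
|---|---|---|
| 10% | 11.5% | 43% |
| 20% | 54% | 78% |
| 30% | 87% | 95% |
| 50% | 99.8% | 99.9% |

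**The case against.** - **The term is undefined.** Section II.F.1 never calls soreness, fatigue or needle pain adverse effects. Items 1 and 3 name excessive sweating, whereas II.F.1 speaks of plain sweating, which suggests that the authors separate ordinary exertion from adverse events. This stands. A reader might infer that routine soreness is bound to stop the study. The text supports only that it could, on a literal reading, and the consequence is an enrolment stop with reassessment, not termination.
- **The two halves partly cancel.** On the literal reading with p of 30% to 50%, at least one of the first four participants is affected with probability 1 − 0.7^4 = 76% to 1 − 0.5^4 = 94%. Enrolment would usually have stopped before the single-event gap opens. This is fair, and it is why the minor-effects half is secondary. It does not close the gap: on the narrow reading, or once enrolment resumes, a single death still does not meet item e by itself.
- **Other safeguards exist.** A reader might infer that a death would go unnoticed, or that a stop would rest on the principal investigator alone. Neither is supported. Item 1 requires immediate notice and IRB reporting where appropriate, and the IRB's policies are not set out here. Individual decisions under item 3 also involve a second person.
- **A broad count is a sensible precaution.** Weight-bearing training after spinal cord injury carries risks, such as fracture or pressure ulcer, that the item 3 list omits. This stands. It argues against confining item e to the item 3 symptoms, which would drop those harms and also a fast or slow heart rate.
- **Part of the safety section was not available.** The text just before item a is absent from the copy reviewed, and the visible numbering runs from 1 to 3. The conclusion is limited to the visible text.

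**Conclusion.** The point holds as a minor defect in a rule that the protocol itself states. The firm part is arithmetic: one heart attack, stroke or death does not by itself meet item e from the fifth participant on, or at any time if the denominator is 19, and the Section V.B rule does not cover it. The gap is a missing pre-stated study-level stop. It is not a lost signal. That minor effects could stop enrolment at 4 of 19 is conditional on a literal reading of an undefined term. The percentages in Steps 3 and 4 rest on assumed rates, independence between participants and, except for the delay check, counting in enrolment order. They show scale only.

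**What to change.** Keep the 20% rule for any adverse effect and add to item e: Enrolment also stops, and training pauses until the principal investigator records the outcome of the reassessment, if any one participant has a heart attack, stroke or death, or another serious event such as a fracture.

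Optionally, state that only transient needle-site pain, ordinary muscle soreness or fatigue, ordinary sweating and mild discomfort do not count towards the 20%. All other adverse effects, including those not listed in item 3, still count. With this option, those mild effects no longer stop enrolment automatically. Without it, nothing that counts now is lost.

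The change is a short amendment to one item. Its cost is a rare pause. Each week costs participants in training 3/24 = 12.5% of their sessions. At three enrolments a month and 56 days of training, about 3 × 56/30.4 = 5.5 people would be in training at once. At 19 over 7 months it is about 5.0. A long pause could also disturb the Aim 2 muscle-activity measure, since Section I.B.5 cites this finding: "The amplitude of EMG activity of leg muscles significantly increased after a period of walk-training and worsened after stopping training." At the assumed 0.1% to 1% for heart attack, stroke or death, a pause would occur in 1.9% to 17.4% of studies, and somewhat more often once other serious events are included.
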